### Postoperative Data Collection

All subjects will be observed in the Postoperative Anesthesia Care Unit (PACU), the Neurointensive Care Unit, and the general medical floor after the operation. Using a 10-cm VAS (where '0' is defined as 'no pain at all' and '10' as 'the worst possible pain'), the subjects' pain score will be assessed every 2 hours after extubation postoperatively while in the ICU, and every 4 hours thereafter, for 72 hours during waking hours, while inpatient or until discharge in those discharged prior to 72 hours post-op. The VAS will be administered by a nurse trained in the technique. Nurses will receive a study guide, to be distributed at the beginning of the study, which provides instructions on obtaining pain scores and GCS assessments. Data will be recorded in the electronic record, as per usual clinical practice. The raters (nurses) and the patients will be blinded to the study group.

All subjects will have their methemoglobin measured once daily for 3 days to monitor for methemoglobinemia while inpatient, or until discharge in those discharged prior to 3 days after surgery.

The Glasgow Coma score (GCS) (Teasdale & Jennett, 1974) will also be assessed at the above time points. Patients with GCS verbal score of <4 will be excluded from statistical analysis because of inability to respond to questions after extubation.

The cumulative doses of narcotics during this time period will also be measured. Intravenous narcotic medications will be given by the nurse taking care of the patient as rescue analgesic, as requested by the patient. If the patient requires more analgesics, the dosage will be increased as needed by the patient following standard clinical guidelines. The nurses will be instructed to administer analgesic according to patient demand. The total rescue analgesic requirement will be noted at the above mentioned time intervals.

The duration of time between the end of the surgical procedure (extubation) and the first administration of rescue narcotic will be recorded.

The total length of ICU stay will be recorded. The total length of time in the hospital until discharge will be recorded.

Does your study use MRI? (CAMRIS is the appropriate contact for all studies involving MRIs)

Yes       No (If No, no CAMRIS review needed)

Check of all that apply:

1.5T MRI

3T MRI

7T MRI

Does the MRI use investigational sequences and/ or coils?

Yes       No       Unsure (if unsure be sure to contact CAMRIS)

Does your study include pregnant women?

(See Pregnancy Clause and Justification)

Yes       No

Does the MRI require the use of Contrast Agents?

(See Contrast Risks)

Yes       No

Does your study involve the exposure to radiation, radiotracers and/or radiological imaging modalities?

Yes       No (If No, no RRSC review is needed)

Will any of the radiation exposure result from procedures that are or could be performed solely as a result of a subject's participation in the research protocol?

Yes       No

Ultrasound

Yes       No

Will your study be using CT Scans? (CACTIS is the appropriate contact for studies involving CT scans)

Yes       No

Studies involving Nuclear Medicine: Will subjects be undergoing any of the following procedures specific to research:

- MUGA
- PET/CT Scan
- Bone /DXA

Check off all of the following procedures that will be performed in your research- each option you select will link to the template language document:

- Apheresis/plasma exchange
- Leukapheresis
- Bone Marrow Biopsy or Aspirate
- Use of AP clinical specimens
- Biopsies- check those which apply
- Blood draw

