### **3.3 Study Measures**

A 10-cm VAS (where '0' is defined as 'no pain at all' and '10' as 'the worst possible pain' will be used to assess subjects' pain score. This will be assessed every 2 hours after extubation postoperatively while the patient is in the ICU, and every 4 hours after the patient has left the ICU, for 72 hours while inpatient, during waking hours, or until discharge in patients discharged prior to 72 hours post-op.

The Glasgow Coma score (GCS) (Teasdale & Jennett, 1974) will also be assessed at the above time points. Patients with GCS verbal score of <4 will be excluded from statistical analysis because of inability to respond to questions after extubation.

The cumulative doses of narcotics during this time period will also be measured. Intravenous narcotic medications will be given by the nurse taking care of the patient as rescue analgesic, as requested by the patient. If the patient requires more analgesics, the dosage will be increased as needed by the patient following standard clinical guidelines. Nursing personnel will be instructed to administer analgesic according to patient demand. The total rescue analgesic requirement will be noted at the above mentioned time intervals.

The duration of time between the end of the surgical procedure (extubation) and the first administration of rescue narcotic will be recorded.

The total length of ICU stay will be recorded. The total length of hospital stay will also be recorded.

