### **3.4 Study Endpoints**

#### **3.4.1 Primary Study Endpoint**

The primary outcome variable is subjective pain score as assessed by the 10-cm Visual Analog Scale (VAS) up to 72 hours post-operatively as per protocol in the Neurological Intensive Care unit at the Hospital of the University of Pennsylvania. Each pain score will be recorded at 2-hour intervals while the patient is in the ICU, and every 4 hours thereafter, up to 72 hours. Pain scores will only be recorded during waking hours.

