#### **4.4 Exclusion Criteria**

- Preoperative GCS  $\leq 13$
- Child ( $< 18$  years of age)
- Inability to understand or use the visual analog scale (VAS)
- Proven or suspected allergy to local anesthetics
- Craniotomy incision extending beyond the field of the block
- Patients chronically (more than 2 wk) treated with narcotic medications
- Previous scalp incision
- Bilateral craniotomies
- Allergies to local anesthetics
- GCS verbal score  $< 4$  after extubation
- Patients whose surgeries extend past 6 hours (will be placed on standard of care and removed from study)
- Patients currently on ergot-type oxytotic drugs, MAOIs, or certain antidepressants
- Lactating Mothers

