## 5.1 Screening

Patients will be screened at the time of surgical consenting. Criteria for inclusion will be that the patient:

- Will be undergoing craniotomy.
- Will receive anesthesia.
- Has anticipated normal neurological function post-operatively.
- Does not have allergies to local anesthetics.
- Is not receiving narcotics pre-operatively.

Other inclusion and exclusion criteria as defined above will also apply

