### **6.2.1 Baseline Data**

Baseline and demographic characteristics will be summarized by standard descriptive statistics (including mean and standard deviation for continuous variables such as age and standard percentages for categorical variables such as gender).

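### No preoperative VAS is scheduled, so the trial forgoes a cheap gain in precision and a check on chance imbalance in pre-existing pain, and the VAS exclusion has no described check

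*Combined protocol and SAP*

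**What the plan says.** Section 3.4.1 defines the endpoint: "The primary outcome variable is subjective pain score as assessed by the 10-cm Visual Analog Scale (VAS) up to 72 hours post-operatively". Section 3.3 sets the timing: "This will be assessed every 2 hours after extubation postoperatively while the patient is in the ICU". The Postoperative Data Collection text, under section 5 and again under 5.2.1, repeats that schedule: "the subjects' pain score will be assessed every 2 hours after extubation postoperatively while in the ICU". Sections 3.4.1 and 4.1 do not mention extubation, but they too give only postoperative times. Visit 1 (5.2.1) consists of randomisation, drug preparation, the block and postoperative data collection.

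On eligibility, 4.4 excludes patients with "Inability to understand or use the visual analog scale (VAS"). Section 5.1 states "Patients will be screened at the time of surgical consenting" and, after its own short list, "Other inclusion and exclusion criteria as defined above will also apply". Allocation follows on the morning of surgery (3.2). The only statement about who gives the scale, "The VAS will be administered by a nurse trained in the technique", stands under Postoperative Data Collection.

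On analysis, 6.2.1 states "Baseline and demographic characteristics will be summarized by standard descriptive statistics", with age and gender as examples. The list of additional data in 8.2 has no pain score. The Study Summary and 6.2.2 name a Mann-Whitney U test for the pain score, and 6.2 names analysis of variance with Bonferroni t-tests. None of them names a covariate.

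**The concern.** A postoperative pain score reflects both pain the patient already had and pain from the operation that the block might relieve. Section 4.5 recruits across indications for elective craniotomy, including tumour and aneurysm, so preoperative head pain may differ between patients. The documents do not say how common it is.

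A baseline value of the outcome is often a useful covariate. Without one, the between-patient variation it would explain stays in the error term, and nobody can check whether the arms happened to differ in pain before surgery. The value cannot be reliably recovered afterwards.

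The second matter is practical. If VAS ability is judged informally at consent, with no stated method or record, a patient who cannot use the scale might be missed until after the block and then have no usable primary data.

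**Working it through.** **Inputs from the documents.** d = 1.01, power 0.8, alpha 0.05 and 10% dropout (6.1); 90 subjects allocated 1:1:1 (Study Summary, 3.2), so 30 per arm and 30 × 0.9 = 27 evaluable.

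**Assumptions, not in the documents.** The correlation r between the preoperative VAS and the per-patient postoperative summary, shown from 0.1 to 0.5; a smaller effect, d = 0.5, for illustration; a two-sided test.

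**The plan's own figure.** n per arm = 2(1.96 + 0.84)²/1.01² = 15.4, so 16 (17 with the t distribution), and 18 to 19 after 10% dropout. This is not the stated 30. Unstated variants come to it or close: one-sided 0.05 gives 13, then 15 per arm, or 30 in two arms; two-sided 0.05/3 with a Mann-Whitney efficiency of 0.864 gives 29 per arm. The present point does not depend on which was meant.

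**Value of the covariate.** Variance removed = r². Equivalent sample-size multiplier = 1/(1 − r²). Power = Φ(d√(n/2)/√(1 − r²) − 1.96), with n = 27.

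| r | variance removed | multiplier | power, d = 1.01 | power, d = 0.5 |
|---|---|---|---|---|
| no covariate | 0% | 1.00 | 96.0% | 45.1% |
| 0.1 | 1% | 1.01 | 96.2% | 45.5% |
| 0.2 | 4% | 1.04 | 96.6% | 46.6% |
| 0.3 | 9% | 1.10 | 97.3% | 48.6% |
| 0.4 | 16% | 1.19 | 98.2% | 51.8% |
| 0.5 | 25% | 1.33 | 99.0% | 56.4% |

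Example: for d = 0.5 and r = 0.5, 0.5 × √13.5 = 1.837; 1.837/√0.75 = 2.121; 2.121 − 1.96 = 0.161; Φ = 56.4%.

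**Chance imbalance between any two arms.** The SE of the difference in mean preoperative VAS, in SD units, is √(2/n).

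| n per arm | SE | chance above 0.3 SD | chance above 0.5 SD |
|---|---|---|---|
| 30 | 0.258 | 24.5% | 5.3% |
| 27 | 0.272 | 27.0% | 6.6% |

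An imbalance of 1.96 SE, reached in about 5% of trials for a given pair, moves the unadjusted contrast by r × 1.96 × 0.258 SD at 30 per arm, if the pre- and postoperative SDs are equal. That is 0.05 to 0.10 SD at r = 0.1 to 0.2, and 0.15 to 0.25 SD at r = 0.3 to 0.5. On an assumed SD of 2 points, the latter is 0.30 to 0.51 points on the 10-point scale.

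**The exclusion.** Set in order, 4.4 states the criterion, 5.1 applies it at consenting, and 3.2 allocates later. So the criterion operates before randomisation. What is absent is a method, a rater or a record.

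**The case against.** The strongest reply is that nothing is biased. A reader might infer that unmeasured preoperative pain distorts the treatment comparison. It does not: randomisation balances it in expectation, and the unadjusted standard error and type I error rate already allow for chance imbalance. That reply stands, and it limits the point to precision and an imbalance check.

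The gain is also uncertain. No document supports a value of r, at r = 0.2 or less the gain is negligible, and at the planned d = 1.01 there is little power left to gain. This stands too. However, the d = 1.01 in 6.1 comes from standard bupivacaine against placebo at 4 to 6 hours. Section 1.1 puts the study's focus on liposomal against standard bupivacaine, for which the plan gives no effect size. If that difference is smaller, precision matters more.

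A reader might also infer that the VAS exclusion cannot be applied until after the block. Section 5.1 does not support that, since staff could explain the scale at consent and judge understanding. Only the method is undescribed.

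Finally, the two-week threshold for chronic narcotic use in 4.4 might be read as admitting shorter-term users, and so as evidence of pre-existing pain. But 5.1 requires that patients not be receiving narcotics before surgery and adds the other criteria to that, so the two can be read as cumulative. The wording should be reconciled, but it does not show that narcotic users are admitted.

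**Conclusion.** The point holds as a cheap improvement to the design; it is not a flaw that threatens validity. No preoperative pain score is described anywhere in the protocol, and no covariate is planned. For r between 0.3 and 0.5, adjustment would be worth 10% to 33% more patients. In power, that is 1 to 3 percentage points at d = 1.01, and about 4 to 11 points at d = 0.5. Below r = 0.3 the gain is slight. Both r and the smaller effect are assumptions.

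How many patients would prove unable to use the scale after allocation cannot be estimated from the documents. A preoperative check would reduce only that loss. It would not affect the removals the protocol already foresees, for a low verbal GCS after extubation or for surgery beyond 6 hours.

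**What to change.** 1. In 5.1 and 5.2.1, add one VAS of current head pain before randomisation, at consent or on the morning of surgery, given in the same way as the postoperative scale. Record it. A patient who cannot complete it meets the existing exclusion and is not randomised.
2. List it in 6.2.1 as a baseline variable, by arm.
3. Define one per-patient VAS summary as the primary variable, and settle which test applies among the Study Summary, 6.2 and 6.2.2. Sections 5.6, 7.4.2 and 9.1 speak of a cumulative score, but 3.4.1 and 6.2.2 do not define one. Until this is done the covariate has no model to enter.
4. Then pre-specify the preoperative VAS as a covariate in the between-arm comparison: ANCOVA, or rank ANCOVA if a rank method is kept. Collecting the score without this step would allow an imbalance check but add no precision.
5. Reconcile the preoperative narcotic wording in 4.4 and 5.1.

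The cost is one question at a contact that already takes place, one data field and one covariate, with no extra visit. The downside is one more item to complete before allocation. The score has to be taken before surgery, so the change helps only patients not yet operated on.

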## 5.1 Screening

Patients will be screened at the time of surgical consenting. Criteria for inclusion will be that the patient:

- Will be undergoing craniotomy.
- Will receive anesthesia.
- Has anticipated normal neurological function post-operatively.
- Does not have allergies to local anesthetics.
- Is not receiving narcotics pre-operatively.

Other inclusion and exclusion criteria as defined above will also apply

## 5.2 Study Intervention

### 5.2.1 Visit 1 (sometimes referred to as the baseline visit)

As described in the study procedures section:

#### Randomization

The Neurosurgery Clinical Research Division (NCRD) will generate a randomization table by computer,

which assigns subjects 1:1:1 to the three groups, in random blocks of 3 and 6. On the morning of the procedure, subjects will be assigned sequentially to the lowest unassigned randomization number.

### Preparation

The anesthesia for each treatment arm will be supplied by the OR pharmacy or the OR Omnicell, as per standard protocol. If the patient is randomized to liposomal bupivacaine (1.33% injection), the OR pharmacy will dispense the medication to the NCRD for transport to the OR for preparation on the field. 20 mL of liposomal bupivacaine will be diluted in 40 mL of sterile, injectable saline (0.9% sodium chloride USP), for a total volume of 60 mL. The surgeon will then draw up the medication for use in a sterile syringe. The patients randomized to bupivacaine (0.25% injection) and placebo (0.9% sodium chloride injection USP) will have the OR nurse obtain the randomized medication from the OR Omnicell per standard practice. 60 mL of the randomized medication will be placed on the sterile field and drawn up into a sterile syringe by the surgeon for use.

### Cranial block administration

The anesthesia protocol will be standardized for all patients. All routine drugs will be administered per standard clinical guidelines as directed by the anesthesiologists. Anesthetic induction and maintenance will be at the discretion of the attending anesthesiologist. Cranial block is performed at the start of the case as standard of care for all craniotomy procedures. Muscle relaxants will be used as needed and reversed at the end of the surgery, based on standard clinical practice.

Per standard of care, after craniotomy, post-operative pain is managed with systemic opiate medications. Certain surgeons in the department (including the PI) perform post-operative cranial blocks to limit post-operative pain and minimize subsequent narcotic use. However, this is not standard of care and is not common practice for many neurosurgeons in the department. Inclusion of a placebo group mirrors the practice of other neurosurgeons within the department who do not perform post-operative blockade unless the operation is long (e.g. >6h). As there is no uniform national standard regarding the use of post-operative local anesthetics, the use of these medications falls within the domain of individual practice patterns. Patients in the placebo arm will share the same risk of postoperative pain as patients in the routine practice of several surgeons.

Under this protocol, the surgeon will administer a cranial block (bupivacaine, liposomal bupivacaine, or placebo), according to a technique previously described by Pinosky et al (Pinosky et al., 1996). The solution for the cranial block will be supplied by the OR pharmacy. The OR nurse will deliver the solution into a sterile container on the sterile field. The solution will be drawn into a syringe for the surgeon to immediately administer. The supraorbital, supratrochlear, zygomaticotemporal, auriculotemporal, postauricular lesser and greater occipital nerve branches on the ipsilateral side of the operation will be

blocked with 5-10 cc of solution (with a maximum of 60 cc at all sites) by needle infiltration. This process generally takes 1-2 minutes. Following this, the general anesthesia is lightened and the patient is extubated in usual fashion.

### Postoperative Data Collection

All subjects will be observed in the Postoperative Anesthesia Care Unit (PACU), the Neurointensive Care Unit, and the general medical floor after the operation. Using a 10-cm VAS (where '0' is defined as 'no pain at all' and '10' as 'the worst possible pain'), the subjects' pain score will be assessed every 2 hours after extubation postoperatively while in the ICU, and every 4 hours thereafter, for 72 hours during waking hours, while the patient is inpatient. Those that are discharged prior to 72 hours will be followed until discharge. The VAS will be administered by a nurse trained in the technique. Nurses will receive a study guide, to be distributed at the beginning of the study, which provides instructions on obtaining pain scores and GCS assessments. Data will be recorded in the electronic record, as per usual clinical practice. The raters (nurses) and the patients will be blinded to the study group.

The Glasgow Coma score (GCS) (Teasdale & Jennett, 1974) will also be assessed at the above time points. Patients with GCS verbal score of <4 will be excluded from statistical analysis because of inability to respond to questions after extubation.

The cumulative doses of narcotics during this time period will also be measured. Intravenous narcotic medications will be given by the nurse taking care of the patient as rescue analgesic, as requested by the patient. If the patient requires more analgesics, the dosage will be increased as needed by the patient following standard clinical guidelines. The nurses will be instructed to administer analgesic according to patient demand. The total rescue analgesic requirement will be noted at the above mentioned time intervals.

The duration of time between the end of the surgical procedure (extubation) and the first administration of rescue narcotic will be recorded.

The total length of ICU stay will be recorded.

#### **5.2.2 End of Study Visit**

The end of study visit will be conducted at the patients' post-operative appointment 4-6 weeks after surgery. No results will be shared at this meeting, and the investigator will not be unblinded. The subject will be debriefed in a standard fashion and his surgical and post-operative care will be reviewed.

#### **5.3 Unscheduled Visits**

Due to the study design, there will be no unscheduled visits.

#### **5.4 Subject Withdrawal**

Subjects may withdraw from the study at any time without impact to their care. They may also be discontinued from the study at the discretion of the Investigator for lack of adherence to intervention or

study procedures or AEs. The Investigator may also withdraw subjects who violate the study plan, to protect the subject for reasons related to safety or for administrative reasons. It will be documented whether or not each subject completes the study. Subjects who withdraw early will have one final visit, at the time of their follow-up appointment, to collect final evaluations and assess adverse events.

#### **5.4.1 Data Collection and Follow-up for Withdrawn Subjects**

Subjects who withdraw consent to participate in the study will be seen for one final study visit. During this visit they will be asked for permission to have the study team look into their survival status via publically available means.

#### **5.5 Early Termination Visits**

There will be no specific termination visit. Should the patient decide to leave the study prior to completion, the standard of care will continue to be administered.

#### **5.6 Safety Evaluation**

A local safety officer will have access to unblinded data, including patient identification and drug group. [name], MD, PhD, has extensive experience with randomized controlled studies, and has served in the capacity of Safety Officer for studies. [name], in collaboration with the study coordinator, will review patient data once five subjects have been enrolled. When 15 additional subjects have been enrolled for a total of 20, [name] will again review the data. Reviews will continue at increments of 20 subjects, at enrollment totals of 40 and 60. Specifically, the Safety Officer will independently examine the primary outcome measure (i.e. cumulative pain intensity scores) and secondary outcome measures (i.e. GCS, narcotic utilization, time to rescue medication, ICU length of stay, hospital length of stay), as well as remain vigilant for any adverse events. If any adverse events are suspected, enrollment will immediately cease, the IRB will be notified, and a meeting between the Safety Officer, PI and study coordinator will take place.

[name] contact information will be provided on the study instruction sheet provided to nurses and available in the patient's chart. If any clinical staff suspects an adverse event, the study sheet provides instructions to contact the IRB and [name] immediately. Additional contact information for the PI, and the study coordinator will be listed for any concerns.

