### **3.2 Allocation to Interventional Group**

The Neurosurgery Clinical Research Division (NCRD) will generate a randomization table by computer, which assigns subjects 1:1:1 to the three groups, in random blocks of 3 and 6. On the morning of the procedure, subjects will be assigned sequentially to the lowest unassigned randomization number. The surgeon performing the procedure and operating room staff will not be blinded to the intervention, since they will see whether the patient is receiving liposomal bupivacaine, bupivacaine or saline. However, all providers obtaining post-operative data from the patients will be blinded as to which treatment the patient received, in addition to the patient themselves.

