## **4 Study Population and Duration of Participation**

### **4.1 Duration of Study Participation**

Study participation will last from the intervention (craniotomy) through the patients stay in the hospital. Participation will officially end at the patient's follow-up visit 4-6 weeks postoperatively, at the end of study visit.

We plan to enroll subjects for 12 months (10/2019-10/2020). We expect to enroll 90 neurosurgical patients during that time. Neurosurgical patients will participate in the experiment through the duration of their stay in the hospital. Typically, these stays are 1-2 weeks in duration. Each patient will report his or her VAS pain score (in increments of 1 from a range of 0 - 10) every 2 hours while in the ICU and every 4 hours after leaving the ICU, for a duration of up to 72 hour postoperatively. GCS scores will also be recorded at 2-hour intervals while the patient is in the ICU. The total length of ICU stay will also be recorded. Once the patient is transferred to the neurosurgery ward, GCS will be documented every 4 to 8 hours.

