### **4.2 Total Number of Subjects and Sites**

This project will aim to recruit approximately 7-8 patients per month (90/year) up to a total of approximately 90 patients across the Department of Neurosurgery. This rate of accrual is based on number of potential candidates available from the current case volume for the Department of Neurosurgery at the Hospital of the University of Pennsylvania. No additional recruitment will be required. The duration of the study and the total number of patients listed above are necessary to adequately detect clinically and statistically significant differences in primary and secondary outcomes. The University of Pennsylvania will be the only study site.

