## **7.3 Relationship of AE to Study**

The PI and safety monitor will be jointly making the determination the relationship of each adverse event to the study procedure. Prior studies have described AE's common to this procedure to be nausea, emesis, and hypotension (Brown et al., 2019). These will be considered to be probably or definitely related to the procedure, after analysis of the data is considered. Other AEs will be determined and characterized on a case by case basis.

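### The listed Safety Officer reviews end at 60 enrolled although 90 are planned, so the plan's own 20-subject increment is not carried through and the last third has no scheduled aggregate review

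*Combined protocol and SAP*

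**What the plan says.** Section 5.6 (Safety Evaluation) gives a local Safety Officer unblinded data with treatment group. The officer, working with the study coordinator, "will review patient data once five subjects have been enrolled". The next review is set by: "When 15 additional subjects have been enrolled for a total of 20". After that, "Reviews will continue at increments of 20 subjects, at enrollment totals of 40 and 60". Each review covers the primary pain outcome, the secondary outcomes (GCS, narcotic use, time to rescue, ICU and hospital stay) and adverse events. Sections 7.4.2 (Data and Safety Monitoring Plan) and 9.1 (Study Monitoring Plan) repeat the schedule with the same totals.

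The planned size is 90. The Study Summary gives that number, section 4.1 says "We expect to enroll 90 neurosurgical patients during that time", and section 4.2 says "up to a total of approximately 90 patients across the Department of Neurosurgery".

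Other safety provisions do not depend on the schedule. Section 5.6 adds: "If any adverse events are suspected, enrollment will immediately cease, the IRB will be notified", followed by a meeting of the Safety Officer, the PI and the coordinator. Section 7.3 says: "The PI and safety monitor will be jointly making the determination the relationship of each adverse event to the study procedure". Section 10.1 requires adverse events of any type to be reported verbally to the IRB and the Study Officer within 24 hours.

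**The concern.** The sentence states a continuing 20-subject rule and then names totals that stop two thirds of the way through enrolment. Staff running the trial will probably work from the named totals, and all three sections name the same ones.

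At stake is the scheduled look at accumulated data during the last third of the trial. Case-by-case reporting is a weak tool for two kinds of signal:

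- **Expected events.** Section 7.3 names nausea, emesis and hypotension as common with this procedure. One more case says little by itself; an excess in one group shows only when events are accumulated by group.
- **Outcomes that raise no report.** A moderate shift in GCS, narcotic use, time to rescue or length of stay need not generate an adverse event report. The scheduled review is the only safety process in the plan that is said to examine these outcomes.

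Section 6.1 says that liposomal bupivacaine has not been studied before for pain after craniotomy, so data accumulating in this trial are an important source of safety information in this setting.

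**Working it through.** **Inputs**

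- Planned enrolment: 90 (Study Summary, 4.1, 4.2).
- Reviews: 5 enrolled, then 15 more, then steps of 20, with 40 and 60 named (5.6, 7.4.2, 9.1).
- Allocation: "which assigns subjects 1:1:1 to the three groups, in random blocks of 3 and 6" (3.2).
- Accrual: 7-8 patients per month (4.2).

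**Step 1. Reproduce the plan's schedule.** 5; 5 + 15 = 20; 20 + 20 = 40; 40 + 20 = 60. The listed totals agree with the stated increments up to 60.

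**Step 2. Carry the same increment on to 90.** 60 + 20 = 80; 80 + 20 = 100, which exceeds 90. The plan's own rule therefore gives exactly one further review, at 80, and it is not listed.

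**Step 3. Patients after the last listed review.** 90 - 60 = 30; 30/90 = 33.3%.

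**Step 4. Per arm.** 30/3 = 10. This is approximate. Both block sizes are multiples of 3, so at 60 randomised the list is either at the end of a block or halfway through a block of 6, and the arms can differ by at most 2.

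**Step 5. Calendar time.** At the midpoint rate, 30/7.5 = 4.0 months. At 8 and 7 per month, 30/8 = 3.75 and 30/7 = 4.3 months.

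**Step 6. Effect of adding 80.** 90 - 80 = 10 patients, 10/90 = 11%, would enrol after the last review during enrolment. A review at completion would leave none outside scheduled review.

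**Step 7. What continues after 60.** The enrolment stop on a suspected adverse event (5.6, 7.4.2, 9.1), the instruction to clinical staff to make immediate contact (5.6, 7.4.2), joint causality assessment (7.3) and 24-hour verbal reporting (10.1) carry no enrolment limit. Only the scheduled aggregate review ends at 60.

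**The case against.** The strongest reply is that oversight does not lapse. As written, a single suspected adverse event in patients 61 to 90 halts enrolment and brings in an officer who can see treatment group. That access is not limited to review dates. The documents do not describe a formal between-arm comparison, still less one confined to the scheduled reviews. All of this stands, and it limits the point to the loss of a planned aggregate look. It does not remove the point, because nothing requires anyone to assemble and examine the accumulated data after 60, and the outcomes that raise no report have no other trigger.

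It can also be said that a rule of continuing in steps of 20 already implies 80. That reading is reasonable, but the sentence names only 40 and 60 in all three places, so it needs to be written down.

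A review at 80 would add only 20/3, or 6 to 7, patients per arm to the 20 per arm seen at 60, so any comparison would stay imprecise. That is true, and it is a reason to call the gap modest.

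A reader might infer three stronger things:

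- **That the last 30 patients have no safety oversight, or that an excess in the liposomal arm would not be looked for.** The continuing provisions in step 7 contradict this.
- **That the harm can be sized by assuming an event rate and computing the chance of a case, or a first case, among an arm's last 10 patients.** That gives the chance of a late case, not of missed harm, because each case would still be reported and assessed.
- **That the schedule was carried over from a 60-patient design.** The totals would fit one, but the documents do not say so.

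**Conclusion.** The point holds as a gap between the listed review schedule and the planned enrolment. Thirty of 90 patients (33%, about 10 per arm, about four months of accrual) enrol after the last scheduled aggregate review, and the plan's own increment would place one more review at 80. The figures assume that enrolment reaches 90 and that the named totals are followed literally.

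The consequence is moderate. Event-driven reporting, the enrolment stop and joint causality assessment cover the whole trial, so the documents do not support a claim of unmonitored patients or of a quantified chance of missed harm. The loss is confined to the scheduled look at slowly emerging imbalances. The primary analysis is not affected. The correction is worth making because it is cheap and removes an inconsistency that appears in three places.

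**What to change.** In sections 5.6, 7.4.2 and 9.1, extend the list so that the totals named after 20 are 40, 60 and 80.

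State in the same place that the added review is for safety and is not the basis of an efficacy decision. This is needed because each scheduled review also examines the primary outcome unblinded, so a fifth review would otherwise add another look at efficacy.

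If a closing review is wanted, schedule it after the last 4-6 week visit, when participation ends under section 4.1. A review tied to the 72-hour pain window would miss later events. The block is given once, at surgery, so a review after the last patient has been treated cannot protect anyone still to receive it. Its purpose is a complete safety record, and the text should say so.

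Cost: one more review by the existing Safety Officer, or two with the closing review, and a short amendment repeated in three sections. Sample size, treatment and the existing event-driven provisions are unchanged.
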